## **4. Study population**

### **4.1 Diagnostic Criteria**

According to the diagnostic criteria of ARDS in Berlin 2012

### **4.2 Inclusion Criteria**

Each subject must meet all inclusion criteria to be eligible to participate in the study.

- (1) Patients who have agreed to participate in the clinical trial and signed informed consent;
- (2) Age 18-80 years old, gender unlimited;
- (3) Patients with ARDS requiring mechanical ventilation;
- (4) Acute right ventricular dysfunction due to ARDS;

### **4.3 Exclusion Criteria**

All baseline subjects meeting any of the exclusion criteria will be excluded from the study.

- (1) Pregnant or lactating women;
- (2) Chronic cardiac insufficiency, pulmonary hypertension and/or right ventricular

enlargement caused by chronic cardiopulmonary disease, cardiogenic shock or after major cardiac surgery before ARDS;

- (3) right ventricular myocardial infarction;
- (4) Uncorrected hypotension, hypoxemia and hypercapnia, or acid-base balance disturbance;
- (5) pre-randomized mechanical ventilation drive pressure  $\geq 18\text{cmH}_2\text{O}$ ;
- (6) rapid arrhythmia;
- (7) pericardial tamponade;
- (8) Pulmonary embolism;
- (9) Severe renal insufficiency;
- (10) Severe liver insufficiency;
- (11) Failure to sign informed consent;
- (12) known allergy to the test drug and control drug;
- (13) Patients who have participated in other clinical trials within 30 days;

#### **4.4 Grouping method of subjects**

Patients will be randomized to treatment group A: intravenously injected levosimendan 12.5mg with 5% glucose injection 50ml configuration at 2ml/h for 24h, or treatment group B: control group with 5% glucose injection 2ml/h for 24h.

The randomization method of the experiment was block randomization and stratification according to the center. The statistical specialty used SAS 9.4 software to generate the blind base of the treatment group randomized according to the 1:1 allocation ratio between the experimental group and the control group. According to the enrollment sequence of patients, random numbers were issued from small to large and groups were assigned. The random number is reproducible, and the set parameters such as the number of centers, section length and seed number are recorded in the blind base.

#### **4.5 Criteria for subject withdrawal**

Early withdrawal All patients who fill in the informed consent form and are screened for qualified randomized entry into the trial are referred to as shedding cases

(shedding and excluding cases should be controlled below 20% of the total number of cases), no matter when they quit for any reason, as long as they do not complete the observation period specified in the scheme. The reasons are as follows: (1) The investigator considered it most beneficial for the patient to terminate treatment due to safety concerns (such as adverse events); (2) Serious protocol violations (any protocol violations will be assessed by the investigator, who will consult the principal investigator of the group leader unit to determine whether they are serious enough to warrant withdrawal from the study); (3) Patients voluntarily terminate the study. Patients are free to terminate the study under any circumstances and will not be discriminated against in their subsequent treatment.

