#### **1.4.6 Discussion**

ARDS is often complicated by right ventricular dysfunction (RVD), the incidence of which can be as high as 64%. The pathogenesis includes elevated pulmonary vascular resistance and right ventricular systolic dysfunction [1-3]. The fatality rate of ARDS patients with RVD increased significantly from 30.6% to 56.3%[4,5]. For ARDS patients with right heart failure, currently available drugs include dobutamine and Milrinone, but dobutamine has a high risk of rapid malignant arrhythmia, increases myocardial oxygen consumption, and large doses will increase the proportion of body and lung circulation, leading to systemic hypotension, which is not conducive to the treatment of ARDS patients with right heart failure [14]. Milrinone also has the effect of increasing myocardial contractility, but its application is limited due to systemic hypotension [14]. While levosimendan increases myocardial contractility, it does not increase myocardial oxygen consumption and does not lead to malignant arrhythmias. Many animal experiments have shown that levosimendan can reduce pulmonary circulation resistance, protect myocardium

during myocardial ischemia, improve right ventricular/pulmonary artery coupling, and improve myocardial energy metabolism. Compared with dobutamine and Milrinone commonly used in clinical practice, levosimendan has more advantages and has fewer side effects on patients [14]. Therefore, the purpose of this study is to provide a more powerful research basis for the use of levosimendan in ARDS patients with right heart failure. Because the drug itself has few side effects of arrhythmia and hypotension, and the protocol has fully considered the management of adverse reactions, the risk to subjects will be minimized even if there is no clinical benefit.

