## **2. Study objective/end point**

The main objective is to (confirm) about whether or not the leosimendan improve mechanical ventilation in patients with ARDS right heart function.

secondary objective is to exploratory whether or not levosimendan reduces mechanical ventilation in patients with ARDS mortality

Primary endpoint: the incidence of RVD after 48h ending of randomization

Secondary endpoint: (1): TAPSE, S ', FAC, RVEDA/LVEDA PVR, RV-PA coupled CI, SVI, SVR, ScvO2 SOFA score after 48h ending of randomization. (2) 28-day mortality rate, in-hospital mortality rate.

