### **3.2 Sample size**

After discussion by clinical experts and combined with the literature results, it is expected that the mean difference and standard deviation between the experimental group and the control group in this study are 20% and 20% respectively.  $\alpha=0.05$  (bilateral), power=0.9, the proportion of experimental group and control group was 1:1, the number of cases meeting the statistical requirements of the experimental group and control group were 23 cases each. Considering the 20% shedding rate, the statistical sample size was 29 cases in the experimental group and 29 cases in the control group, and a total of 58 subjects were enrolled.

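### The 48 h echo endpoint gives no value to a patient who dies before it; read literally, section 4.5 makes that patient a shedding case, leaving a survivors-only comparison

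*Protocol*

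**What the plan says.** Protocol section 1.1.1 defines RVD by four echo criteria: RVEDA/LVEDA above 0.6, TAPSE below 16 mm, S' below 10 cm/s, or RV FAC below 35%. Death is not a component. Section 2 gives "Primary endpoint: the incidence of RVD after 48h ending of randomization", and section 7.1 also places the assessment at 48 h. Mortality at 28 days and in hospital are separate secondary endpoints.

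Section 4.5 treats randomised patients as shedding cases "no matter when they quit for any reason, as long as they do not complete the observation period specified in the scheme". It then lists three reasons: termination by the investigator for safety, serious protocol violation, and voluntary termination. Death is not on the list, and it is not expressly excluded. The observation period is not defined there.

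Section 3.2 arrives at 23 evaluable patients per arm and continues: "Considering the 20% shedding rate, the statistical sample size was 29 cases in the experimental group and 29 cases in the control group". Section 9 names three analysis sets and asks for shedding cases to be listed with their causes. Section 6 makes a serious trial-related adverse reaction a ground for leaving the study, and section 10.2 ends study tests once a patient withdraws.

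**The concern.** A death in the first 48 h is at least as bad an outcome as persistent RVD, yet it produces no endpoint value. If such patients fall into the shedding pool, each arm's RVD rate is a rate among its own survivors, and the two groups of survivors are no longer the groups formed by randomisation. Section 1.4.2 expects heart-rate and blood-pressure effects from the study drug, so equal early mortality cannot be taken for granted. If the patients who die are mostly those who would have been counted as RVD, the arm that loses more of them shows a lower RVD rate.

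This is a matter of endpoint definition. The definition of RVD, the time of assessment and the meaning of shedding are all fixed in the protocol.

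**Working it through.** **The plan's own figure.** Section 3.2 gives a mean difference of 20% and SD of 20% (standardised effect 1.0), two-sided alpha 0.05, power 0.90 and 1:1 allocation. With the noncentral t distribution, power is 0.8997 at 22 per arm and 0.9125 at 23, so 23 per arm is reproduced. Then 23 / (1 − 0.20) = 28.75, rounded up to 29 per arm, or 58 in all. The allowance is 29 − 23 = 6 per arm, and dividing by 0.8 treats those six as giving no primary data.

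**How many early deaths fit in the allowance.** The protocol gives no 48 h mortality. Assumed rates of 2% to 20% give 29 × 0.02 = 0.6 to 29 × 0.20 = 5.8 deaths per arm, all within six.

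**Effect on the comparison.** For one arm, let d be deaths before the 48 h TEE and r be survivors with RVD. The survivors-only rate is r / (29 − d). With death counted as failure it is (r + d) / 29. All counts below are assumptions, given as levosimendan v control; a negative difference favours levosimendan.

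| Deaths | Survivors only | Difference | Death counted as failure | Difference | Shift |
|---|---|---|---|---|---|
| 2 v 2 | 13/27 v 18/27 = 48.1% v 66.7% | −18.5 | 15/29 v 20/29 = 51.7% v 69.0% | −17.2 | about 1 |
| 4 v 1 | 12/25 v 18/28 = 48.0% v 64.3% | −16.3 | 16/29 v 19/29 = 55.2% v 65.5% | −10.3 | about 6 |
| 6 v 0 | 14/23 v 18/29 = 60.9% v 62.1% | −1.2 | 20/29 v 18/29 = 69.0% v 62.1% | +6.9 | about 8 |

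Only the last row changes sign. With the same totals but 6 v 1 deaths, the survivors-only rates are 14/23 = 60.9% v 17/28 = 60.7%, and the sign does not turn.

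**No true difference.** Let RVD or death be 18/29 in both arms. With 6 v 0 deaths, the survivors-only rates are 12/23 = 52.2% v 18/29 = 62.1%, a false gain of 9.9 points. With 3 v 0, they are 15/26 = 57.7% v 62.1%, a false gain of 4.4. With 6 v 6, the difference is 0. In the no-difference cases run, Fisher's exact p was never below 0.41, so the estimate is biased but the bias alone does not produce significance.

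**The case against.** Four points can be made on the other side.

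- **Exclusion is not written.** Section 4.5 sets a label, section 9 only lists the shedding cases, and an allowance for loss in a sample size is not an analysis rule. A statistical analysis plan, not shown here, could define the full analysis set and place early deaths in it. This stands: the survivors-only rate is an inference. But keeping the dead in the denominator without an endpoint rule does not help. Counted as free of RVD, the 6 v 0 no-difference case becomes 12/29 = 41.4% v 62.1%, a false gain of 20.7 points.
- **Section 4.5 is about patients who quit, and its reasons omit death.** This also stands; the literal reading is one of two. On the other reading, a patient who dies before 48 h still has no primary value and no stated place in the endpoint.
- **The abstract words the endpoint as RVD within 48 hours, so an earlier TEE might supply a value.** Sections 2 and 7.1 do not say this, and since RVD is an entry criterion, an earlier reading is hard to interpret as the outcome.
- **Early deaths are not hidden.** They enter the 28-day and in-hospital mortality endpoints. This stands and limits the harm to the primary comparison.

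A reader might also infer that the 56.3% fatality with RVD in section 1.4.6 contradicts the 20% ceiling on shedding in section 4.5. The documents do not support that. The figure has no time horizon, and section 1.1.1 ties it to COVID-19 ARDS, so it cannot be set against losses before a 48 h assessment.

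**Conclusion.** The concern holds in a limited form. The endpoint has no value for a patient who dies before the 48 h TEE, the literal wording of 4.5 takes that patient in as a shedding case, and 3.2 plans on no primary data from such cases. Followed that way, the plan compares RVD among 48 h survivors and favours an arm with more early deaths.

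The size rests on assumed death and RVD counts: about 1 point with equal small numbers of deaths, about 6 points with 4 v 1, and about 8 points with a change of sign at 6 v 0. A reader might conclude that the plan would make a harmful drug look beneficial. The documents do not show this: they give no early mortality by arm, material bias needs unequal early deaths, and in the cases worked the reversal needed all six deaths in one arm. This is a cheap improvement worth making before outcomes are known, not a defect that invalidates the trial.

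**What to change.** In sections 2 and 7.1, define the primary outcome as RVD on the 48 h TEE or death from any cause before that TEE, and report the two components separately by arm. Carry the same wording into the abstract, so that its within-48-hours phrase no longer differs. In section 4.5, state that death is an outcome and not shedding, and that the observation period for the primary endpoint ends at 48 h.

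The cost is wording only. Deaths are already followed for the 28-day mortality endpoint, and the calculation in 3.2 is not altered by this change. The downside is that the endpoint becomes a composite, and deaths unrelated to the right heart add some noise; reporting the components separately keeps that visible. The change does not settle how living patients without a 48 h TEE are handled, which can be left to the statistical analysis plan.

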## 5. Research interventions

### 5.1 Description of the study intervention

Patients will be randomized to treatment group A: intravenously injected levosimendan 12.5mg with 5% glucose injection 50ml configuration at 2ml/h for 24h, or treatment group B: control group with 5% glucose injection 2ml/h for 24h.

Only when the clinician is satisfied that adequate fluid resuscitation has been achieved can the drug be investigated for pumping. Both groups were injected at a constant rate of 2ml/h starting at 8am after randomization. If there was no significant hypotension or tachycardia, the injection was completed at 24h. Any incipient hypotension can be treated with fluid replacement or/and pressors depending on the actual condition. During the entire infusion period, systolic blood pressure  $< 80\text{mmHg}$  and heart rate  $> 140\text{bpm}$  is sustained for more than 10min or the heart rate increases by more than 25bpm, the pumping rate should be reduced or discontinued until hypotension and tachycardia disappear, and the dose should be halved when intravenous pumping is restarted [15]. Depending on clinical condition, clinician can use fluids and norepinephrine to maintain MAP  $\geq 70\text{mmHg}$ , dobutamine was used to maintain CI  $> 2.5\text{L/min/m}^2$ .

All patients received right cardiac protective mechanical ventilation, tidal volume (VT) 4-8ml/kg, platform pressure  $\text{P}_{\text{plat}} \leq 27\text{cmH}_2\text{O}$ , driving pressure  $<$

18cmH2O, the optimal PEEP was titrated by lung compliance method after lung reexpansion; Adjust the respiratory rate (RR) not more than 35 times/min to  $\text{PaCO}_2 < 48\text{mmHg}$ ,  $\text{FiO}_2$  levels were adjusted to maintain  $\text{SpO}_2$  88%-95% and  $\text{PaO}_2$  55-80mmHg. In hypotension (mean arterial pressure  $< 60\text{mm Hg}$ ) or in the case of pneumothorax, PEEP can be further adjusted according to the patient's needs; If  $\text{PaO}_2/\text{FiO}_2 < 150$ ,  $\text{FiO}_2 > 0.6$ . Based on the clinician's judgment, PEEP levels can be further titrated by optimal compliance after lung recruited. Check the  $\text{P}_{\text{plat}}$  and drive pressure at least 4 hours after each change in PEEP or VT. If lung reexpansion and PEEP titration do not maintain oxygenation or hypercapnia occurs, prone position may be performed for more than 16 hours per day; If the prone position does not improve oxygenation and correct hypercapnia, VV-ECMO can be considered if one of the following conditions is met:  $\text{PaO}_2/\text{FiO} < 50\text{ mmHg}$  for more than 3 h;  $\text{PaO}_2/\text{FiO}_2 > 80\text{ mmHg}$  for more than 6 h; Or arterial blood  $\text{pH} < 7.25$  accompanied by  $\text{PaCO}_2 > 60\text{ mmHg}$  over 6 h[16].

All patients were titrated with sedative analgesic agents according to sedative analgesic targets. If  $\text{PaO}_2/\text{FiO}_2 < 150$ , then deep sedation, RASS-4 points to reduce respiratory drive; If  $\text{PaO}_2/\text{FiO}_2 > 150$ , light sedation, RASS 0 ~ -2, maintain  $\text{RR} < 30$ ,  $\text{VT} < 10\text{ml/kg}$ . All patients maintained COPT score of 0 for titrated analgesics.

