### **1.4.4 Known potential benefits**

The occurrence of ARDS related right heart failure is not uncommon, and the

combination of acute right heart failure will lead to hemodynamic failure and significantly increase mortality in mechanical ventilation ARDS patients. At present, there is no clear and effective drug for ARDS right heart failure in clinical practice, and there is also a lack of relevant clinical evidence. The results of this study will provide certain clinical evidence for drug treatment of right heart failure in patients with mechanical ventilation ARDS, and may even help to reduce the mortality of ARDS patients and improve the prognosis.

Of course, the study design for this subject will minimize the need for subjects to be exposed to risk. First, avoid all contraindications of levosimondan use in the drug label and exclude patients who already have rapid arrhythmia or hypotension. The management of possible risks has been elaborated in the medication procedure. Vital signs of patients will be monitored in real time throughout the experiment, and adverse reactions will be handled according to the experimental procedure to minimize risks.

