## 6. Research steps

- (1) Patients eligible for inclusion in the study were screened and informed consent was signed.
- (2) Patients were randomly assigned to the experimental group or the control group. Vital signs and hemodynamic parameters were recorded 1 hour before administration, and related indexes such as cardiac function and pulmonary circulation were detected by transesophageal ultrasound, as well as arterial blood gas, central vein blood gas, blood routine, liver and kidney function, electrolyte, myocardial enzyme profile and BNP were detected by blood sampling.
- (3) According to the study protocol, all subjects in the two groups began administration at 8am, and 8am vital signs, arterial blood gas, central vein blood gas,

blood routine, liver and kidney function, electrolytes, myocardial enzyme profile and BNP during medication period and the first 24 hours after medication completion were recorded. The related indexes of cardiac function, pulmonary circulation and hemodynamics were monitored by transesophageal ultrasound. Study withdrawal/early termination: Family members refuse to continue treatment if: Family members withdraw from the study; In the presence of experimental-related serious adverse reactions.

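### Dosing starts at a fixed clock time after randomisation, and no rule links the pre-dose reading to eligibility or to the start: the gap is complete for rapid arrhythmia, partial for hypotension and gas disturbance

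*Protocol*

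**What the plan says.** - **Section 1.4.4** names the means of limiting risk: respect the contraindications in the drug label, and "exclude patients who already have rapid arrhythmia or hypotension".
- **Section 4.3** states: "All baseline subjects meeting any of the exclusion criteria will be excluded from the study". Baseline is not defined. Exclusion (4) reads "Uncorrected hypotension, hypoxemia and hypercapnia, or acid-base balance disturbance" and exclusion (6) reads "rapid arrhythmia". Neither carries a time point. Exclusion (5), on driving pressure, is already tied to the time before randomisation.
- **Section 6** gives the order of events. Step (1) is screening and consent. Step (2) opens with random assignment and continues: "Vital signs and hemodynamic parameters were recorded 1 hour before administration", together with transesophageal echocardiography (TEE) and blood sampling that includes arterial gas. In step (3), "all subjects in the two groups began administration at 8am".
- **Section 5.1** sets one condition before the pump starts: "Only when the clinician is satisfied that adequate fluid resuscitation has been achieved can the drug be investigated for pumping". The next sentence fixes the time: "Both groups were injected at a constant rate of 2ml/h starting at 8am after randomization". The section also provides for treating hypotension with fluids or pressors, and has a rule for reducing or stopping the infusion that applies while it is running.
- **Section 4.5** lets the investigator end treatment on safety grounds. It counts any randomised patient who does not complete the observation period as a shedding case.

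**The concern.** An exclusion protects patients only at the moment it is checked. Here the check belongs to baseline, the arm is then assigned, and dosing waits for a clock time. The patients are ventilated, have ARDS with right ventricular dysfunction, and can change within hours. The protocol schedules a reading 1 hour before dosing that would show much of that change, but gives no instruction on what to do with it.

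Two things are at stake. One is consistency with the protocol's own risk argument in section 1.4.4. The other is the randomised comparison. If section 4.3 is taken to apply at the pre-dose reading, patients leave the study because of their condition after the arm is assigned, and the protocol does not say that those who decide are masked to the arm. The baseline TEE, listed in the same step, also comes after assignment as written.

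**Working it through.** The protocol gives no figure on this point to reproduce, so the check sets the sections side by side. The only arithmetic concerns the wait and the loss allowance.

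**1. Order of events.** Section 6 lists consent, random assignment, the reading at 1 hour before administration, then dosing at 8am. Section 5.1 agrees that 8am comes after randomisation. As listed, the arm is known before the pre-dose reading is taken.

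**2. Length of the wait.** Let h be the clock hour of randomisation, and assume that the next 8am is meant. Then wait = (8 − h) mod 24 hours. The protocol does not give h, so these are scenarios:
- Randomisation spread evenly over 24 hours: from just above 0 to 24 hours, mean 12 hours.
- Randomisation at 9am: 8 − 9 + 24 = 23 hours. At 5pm (h = 17): 8 − 17 + 24 = 15 hours. Spread evenly between the two: mean (23 + 15)/2 = 19 hours.
- Randomisation at 7am: 8 − 7 = 1 hour, and the problem nearly vanishes.

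**3. What stands between assignment and the start of the pump.**
- *Rapid arrhythmia (exclusion 6).* The fluid condition in section 5.1 does not mention heart rate or rhythm. The heart-rate rule acts only during infusion. As worded, it needs systolic pressure below 80 mmHg and heart rate above 140 bpm for more than 10 minutes, or a rise of more than 25 bpm. A patient already in a fast rhythm at 8am with systolic pressure above 80 mmHg meets neither part unless the rate rises further. No rule specific to this condition applies before the start.
- *Hypotension (exclusion 4).* Only uncorrected hypotension is excluded. Section 5.1 requires adequate fluid resuscitation before the start and provides for fluids and pressors. The gap is partly covered.
- *Hypoxaemia, hypercapnia, acid-base disturbance (exclusion 4).* Again only uncorrected states count, and section 5.1 sets ventilation targets that work towards correction. The fluid condition does not address gas exchange. The gap is partly covered.

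**4. The two possible outcomes.** Suppose a patient newly meets exclusion (4) or (6) after assignment.
- If section 4.3 is spent once baseline has passed, section 5.1 allows dosing, contrary to the purpose stated in section 1.4.4.
- If section 4.3 still applies, the patient is removed after allocation. Section 10.2 stops study tests for a patient who withdraws, and nothing says that a patient removed in this way still has the 48-hour TEE. Such losses draw on the allowance in section 3.2: 23/(1 − 0.20) = 28.75, rounded up to 29, which leaves 29 − 23 = 6 per arm.

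No section says which outcome is intended.

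**The case against.** The strongest reply is that this is an omission and not a contradiction. Eligibility is judged at baseline, and bedside care is then left to clinicians. Safeguards do exist: the fluid condition, correction of hypotension and gas exchange, real-time vital-sign monitoring and label contraindications in section 1.4.4, and the investigator's power in section 4.5 to end treatment. Section 6 also places randomisation and the pre-dose reading in the same step, so the interval may be short. How an undosed patient is analysed is commonly left to the statistical analysis plan.

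Much of this stands. A reader might infer that the protocol requires study drug to be started in anyone who has come to meet an exclusion. The documents do not support that: the start is conditional on fluid status, exclusion (4) covers only uncorrected states, the label is to be respected, and the investigator may intervene. A reader might also infer that a sizeable share of the 58 patients would be affected. The protocol gives no rate from which to say so, and the wait of up to 24 hours rests on reading the start as the next 8am. The analysis of undosed patients is not counted as a defect here.

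What the reply does not remove is the sequence. The safeguards are discretionary or concern other variables, and none re-applies the exclusions. Using the discretion in section 4.5 can itself turn a randomised patient into a shedding case. For rapid arrhythmia, nothing before the start refers to rate or rhythm.

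**Conclusion.** The point holds in a limited form. The protocol fixes the order badly: assignment precedes the pre-dose reading, and that reading is tied neither to eligibility nor to the decision to start. The gap is complete for rapid arrhythmia and partial for hypotension and gas disturbance. A patient who newly meets an exclusion in the interval is either dosed against section 1.4.4 or removed after allocation.

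The order of events and the lack of a link rest on the text alone. The length of the wait (up to about 24 hours) rests on the assumption of the next 8am and on randomisation times that are not given. The number of patients cannot be estimated. Exclusion (5) is not affected. The change is worth making because it is cheap, not because a large effect has been shown.

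**What to change.** - Reconcile sections 1.4.4, 4.3, 5.1 and 6 on when the exclusions are judged, and define baseline.
- Reorder step (2) of section 6 so that the random number is issued after the pre-dose reading already scheduled. Eligibility and baseline values, including the baseline TEE, then come before assignment, and few patients can change status between assignment and dosing.
- State that a randomised patient who is not dosed is still followed in the assigned arm for the 48-hour TEE and for mortality.

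Whether and when such a patient is dosed is for the investigators to settle. No dosing rule is proposed here.

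The cost is a change of wording and a tighter schedule. The blood gas result, the eligibility decision, assignment and drug preparation must all fit into the hour before 8am. Section 6 lists vital signs at that reading but does not name an ECG, so the investigators should confirm that rhythm is available from the existing monitoring.

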### **1.4.2 Probability of injury**

the possibility of subject harm may involve adverse effects associated with levosimendan. Clinically possible adverse effects are increased heart rate or temporary and slight decrease in blood pressure, which can be treated with dose reduction or withdrawal and symptomatic management.

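### The only numeric trigger for cutting the study infusion (section 5.1) requires hypotension and tachycardia together, or a heart-rate rise, which does not fit the completion sentence or section 1.4.2

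*Protocol*

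**What the plan says.** Protocol section 5.1 sets a constant infusion of 2 ml/h in both arms and then deals with haemodynamic reactions in four steps:

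- **Completion:** "If there was no significant hypotension or tachycardia, the injection was completed at 24h".
- **Supportive treatment:** "Any incipient hypotension can be treated with fluid replacement or/and pressors depending on the actual condition".
- **Trigger for the infusion:** "systolic blood pressure $< 80\text{mmHg}$ and heart rate $> 140\text{bpm}$ is sustained for more than 10min". From the duration onward, the full sentence reads "is sustained for more than 10min or the heart rate increases by more than 25bpm, the pumping rate should be reduced or discontinued".
- **Recovery and restart:** the change lasts "until hypotension and tachycardia disappear, and the dose should be halved when intravenous pumping is restarted".

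The same paragraph lets the clinician use fluids and norepinephrine to keep mean arterial pressure at 70 mmHg or above.

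Section 1.4.2, on the probability of injury, describes the expected adverse effects as "increased heart rate or temporary and slight decrease in blood pressure, which can be treated with dose reduction or withdrawal and symptomatic management".

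The risk/benefit text depends on these provisions. Section 1.4.4 says that the management of possible risks is set out in the medication procedure. Section 1.4.6 says that the protocol has fully considered how adverse reactions are managed.

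**The concern.** Hypotension and a raised heart rate are the two adverse effects named in section 1.4.2. The trigger sentence in 5.1 is the only place where the protocol puts numbers on when the infusion must be reduced or stopped. As worded, low pressure counts only when heart rate is also above 140 bpm, whereas a heart-rate rise of more than 25 bpm counts alone. The completion sentence and section 1.4.2 join the two effects with *or*.

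At stake is whether investigators at different centres apply the same rule to the same patient, and whether the risk/benefit section can rely on a rule that has two readings. It is a question of safety conduct and of consistent exposure before the 48 h assessment.

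**Working it through.** No sample size, power or event figure bears on this point, so the check is of the rule's logic.

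**Inputs (section 5.1).** A = systolic pressure < 80 mmHg; B = heart rate > 140 bpm; A and B together sustained for more than 10 min; C = heart-rate rise > 25 bpm.

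**The rule as written:** reduce or discontinue if (A and B) or C.

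**The rule if the conditions applied singly:** reduce or discontinue if A or B or C.

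Three yes/no conditions give 2 × 2 × 2 = 8 combinations:

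| A: SBP < 80 | B: HR > 140 | C: rise > 25 | As written | Applied singly |
|---|---|---|---|---|
| no | no | no | no change | no change |
| **yes** | **no** | **no** | **no change** | **change** |
| **no** | **yes** | **no** | **no change** | **change** |
| yes | yes | no | change | change |
| any | any | yes (4 combinations) | change | change |

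The readings differ in two of the eight: isolated hypotension, and heart rate above 140 bpm with a rise of 25 bpm or less and systolic pressure of 80 mmHg or more.

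**How much the joint limb adds.** If heart rate exceeds 140 bpm and has risen by 25 bpm or less, the reference rate was above 140 − 25 = 115 bpm. From any reference rate of 115 bpm or lower, a heart rate above 140 bpm already meets C. Taking the pre-infusion rate as the reference (an assumption, since the trigger sentence names none), the blood-pressure criterion can affect the decision only in patients who start above 115 bpm. For everyone else the literal rule is a heart-rate rule.

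**Against the other passages, for a patient with isolated systolic pressure below 80 mmHg:**

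- Trigger sentence: not met, so no change of rate is required.
- Completion sentence: unchanged completion is stated only for patients with neither effect. By implication, significant hypotension alone takes the patient out of that group.
- Section 1.4.2: a fall in blood pressure alone, even a slight one, is an effect for which reduction or withdrawal is available.
- Recovery clause: it joins the two effects with *and*. After a trigger on heart-rate rise alone there may be no hypotension to disappear, so *and* may be used loosely as a list here. The clause does not settle which reading of the trigger is meant.

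**The case against.** The case for leaving the text alone has substance.

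- **Hypotension is not left unmanaged.** A reader might infer that a site following the rule would do nothing about severe isolated hypotension. The documents do not support that. Section 5.1 allows fluids and pressors for any incipient hypotension, and norepinephrine to support mean arterial pressure. Section 4.5 lets the investigator end treatment for safety, and section 1.4.4 provides real-time monitoring of vital signs. This objection stands, and it limits the point to the mandatory change of infusion rate. These provisions are discretionary, however, and do not say when the rate must change.
- **The passages are not opposite commands.** A reader might infer outright contradiction. Section 1.4.2 is a risk summary and is only permissive. The completion sentence leaves significant hypotension undefined, so the numeric rule could be read as defining it, and nothing forbids reducing the rate in isolated hypotension. This also stands: the passages fit badly and point different ways, but none prohibits what another requires.
- **The surrounding text is not uniformly *or*.** This is correct, since the recovery clause uses *and*. It is a reason to include that clause in the reconciliation.
- **No bias between arms is shown.** A reader might infer that centres reading the rule differently would distort the treatment comparison. Randomisation is stratified by centre (section 4.4), the comparison between groups uses a CMH test that considers centre (section 9), and the same rule applies to both arms. Different readings could make exposure vary between centres, but the documents give no basis for a bias or for sizing the difference in dose.
- **The wording may be a translation artefact.** It may be, but investigators have only the text in front of them.

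**Conclusion.** The point holds in a limited form. The trigger in section 5.1 is conjunctive as written. Isolated systolic pressure below 80 mmHg never triggers a change in the infusion, and neither does heart rate above 140 bpm with a rise of 25 bpm or less and systolic pressure of 80 mmHg or more. That does not fit the completion sentence in the same paragraph or section 1.4.2, which treat either effect alone as a reason to alter the infusion, the first by implication and the second permissively.

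The size is logical: two of eight combinations. It says nothing about how many patients are affected, because the documents give no frequency for either state. The 115 bpm figure rests on taking the pre-infusion heart rate as the reference.

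The sentence is worth correcting because it is the protocol's only numeric rule for changing the infusion and because sections 1.4.4 and 1.4.6 rely on it. The missing duration and reference rate for the 25 bpm limb are secondary. Section 6 records vital signs 1 hour before administration, which offers a natural reference.

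**What to change.** Reconcile the trigger sentence in section 5.1 with the completion sentence, the recovery clause and section 1.4.2. State:

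- whether the blood-pressure and heart-rate conditions apply singly or jointly;
- which conditions the 10 min duration covers;
- as a smaller clarification, the heart rate from which the 25 bpm rise is measured.

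Use the same wording in every place. Which clinical rule to adopt is for the sponsor and investigators. The cost is a clarified sentence in 5.1, matching wording in 1.4.2 and a note to the three centres. It needs no extra patients or data.
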